8.2 Sample Size Determination

The primary endpoint of this study is to evaluate the proportion of patients reaching target levels (8-10 ng/ml) on day 3 and day 7 after kidney transplantation.

We calculated that a total study population of 260 patients (pharmacogenomics group = 130; control group = 130 patients) would be sufficient to provide a statistical power of 90% to detect a significant difference between the two groups, on the basis of a two-sided χ^2 test, a significance level of 5%, a frequency of approximately 50% for the *CYP3A5*3/*3* genotype, and a 40% and 60% frequency of the primary endpoint in the control and pharmacogenomic group (Thervet et al. 2010), respectively. Because of the nature of the study design we anticipate a small rate of sample dropout (<5%), which should not appreciably impact the power of the study.

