8.3 Statistical Methods

All analyses will be performed on the basis of the ITT principle. Unless stated otherwise, the term “descriptive statistics” will refer to the number of subjects, mean, median, standard deviation, minimum, and maximum for continuous data and to frequencies and percentages for categorical data. Categorical variables will be summarized as counts and percentages. All statistical parameters (eg, mean, median, standard deviation) will be tabulated together with their corresponding confidence intervals (CIs) and/or standard errors.

Continuous variables will be summarized as medians with first to third quartiles. Appropriate conventional statistical analyses will be used to assess the primary and secondary endpoints. Categorical data will be compared using χ^2 or Fisher’s exact test, as appropriate; some comparisons will require correction for potential confounders such as race/ethnicity; these will be performed using the Cochrane-Mantel-Haenszel test. Continuous variables will be compared using the Wilcoxon test or the t-test. The incidence of an adverse outcome (ie, graft rejection, graft loss, renal impairment, tacrolimus toxicities, and death) will be estimated using Kaplan-Meier curves. Depending on the distribution of the data, time-to-event (ie, time to reach therapeutic target range) analysis will be performed using an appropriate parametric, nonparametric, or semi-parametric survival analysis method. An ANOVA model may be utilized and tabulated along with the CIs. During the analysis, if a possible confounding variable was identified, the variable will be measured and entered into the analysis as a covariate.

Confounding factors that may impact tacrolimus response include race, age, and disease characteristics. It is possible that there may be differences in baseline demographics and disease states between the pharmacogenomic and control group. To minimize the potential impact of confounding variables on treatment response, an overall matching strategy has been incorporated into the design of the study. Please see [Section 8.4](#) for more information regarding the matching strategy.

The exploratory endpoints will be analyzed using descriptive statistics. No formal statistical testing is planned at this time.

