8.4 Matching Strategy

As there are confounding variables, including age, race and disease state that may impact the results of the study, our study design incorporates an overall matching strategy, so that we can identify a well-matched control group. First, to control for differences in care over time, patients in the pharmacogenomic group will be matched to controls enrolled from 2010 to present. This time period was selected as there had been no major changes in standard of care or treatment regimen since 2010. After eligibility is met, control patients will be selected to match the pharmacogenomic group using a computerized matching algorithm that has been optimized to match baseline demographic and disease characteristics that have been identified a priori as likely to influence the treatment response to tacrolimus. To balance the trade-off between minimizing bias and maximizing matched sample size, a systematic approach will be conducted to identify the number of matched control patients for each patient in the pharmacogenomic group. This approach will include the following steps: 1) run the desired matching algorithm, starting with 1:1 (one control to one patient in the pharmacogenomic group) matching and iterating until the maximum desired number of potential controls per treated subject is reached; 2) for each iteration, test for covariate balance; and 3) generate numeric summaries and graphical plots of the balance statistics across all iterations in order to determine the optimal number (Linden and Samuels 2013).

The selection of patients for the control group using a matching algorithm will be conducted by an independent statistician in a blinded and unbiased manner. The statistician will have no knowledge of survival outcome, other outcome data, and genotype.

9 Safety and Adverse Events

Safety will be assessed throughout the study by evaluating physical exam, clinical chemistry, urinalysis, hematology, renal function, and incidence of adverse events (ie, graft rejection, graft loss, renal impairment, drug-related adverse events, tacrolimus toxicities, and death).

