9.5 Interim Analysis

An interim analysis will be performed on the primary endpoint when 30% of eligible patients have been enrolled and have completed the 6 months follow-up. The interim analysis will be performed by an independent statistician who is blinded for the subjects' treatment allocation.

Some of the questions that will be evaluated during the interim analysis will include:

- Is there an unexpectedly high rate of severe or life-threatening adverse events?
- Is the outcome of the trial treatment comparable with that of previous studies?

- Do the results of the interim analysis prove statistically significant differences between the trial treatments that exceed the differences defined by the statistical guidelines of the trial?

10 Data Handling and Record Keeping

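### Section 8.3 makes an unadjusted chi-square the default for a non-randomised, matched comparison and leaves covariates to be found during the analysis; the matching variables of 8.4 should be listed and fixed as the primary adjustment set

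*Combined protocol and SAP*

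**What the plan says.** Section 8.2 claims that 130 patients per group "would be sufficient to provide a statistical power of 90% to detect a significant difference between the two groups". The basis is a two-sided chi-square test at 5%, with 40% attainment in controls and 60% in the pharmacogenomic group. Section 8.3 covers primary and secondary endpoints together and assigns categorical data to chi-square or Fisher's exact test.

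On adjustment, Section 8.3 makes three statements:
- "some comparisons will require correction for potential confounders such as race/ethnicity", by a Cochran-Mantel-Haenszel test. It does not say which comparisons.
- "During the analysis, if a possible confounding variable was identified, the variable will be measured and entered into the analysis as a covariate". It gives no candidate list and no entry criterion.
- "Confounding factors that may impact tacrolimus response include race, age, and disease characteristics". These are named as reasons for matching, not as terms in a model.

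Section 8.4 describes an algorithm that matches on "baseline demographic and disease characteristics that have been identified a priori as likely to influence the treatment response to tacrolimus" and a procedure to "identify the number of matched control patients for each patient in the pharmacogenomic group". It refers to age, race and disease state, but does not itemise the disease characteristics or say that the matching variables, or the matched sets, enter the primary test.

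Section 4.3 adds prospective controls: enrolled patients transplanted before their genotype result was available. They join the control group by that event, not through the matching algorithm.

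**The concern.** Section 4.2 states that a randomised design was not feasible, so the group difference rests on how well known predictors of trough level are balanced or adjusted for. Section 8.3 itself accepts that the groups may differ at baseline. Two weaknesses follow.

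First, the default test ignores the variables used to build the control group. Any imbalance that the algorithm leaves, or that unmatched prospective controls bring in, passes straight into the estimate. Where matching succeeds, the test ignores the correlation it creates, and its standard error is too large.

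Second, the one route to adjustment opens only once the analysis is under way and has no stated rule. A reader of the final report could not tell whether the adjustment set was settled before or after outcomes were seen. Yet Section 8.4 says the relevant characteristics were already identified, so the list should exist. It has only to be written down and used.

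**Working it through.** **1. The plan's own figure.** Inputs from Section 8.2: 40% vs 60%, two-sided 5%, 90% power, equal groups.

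n = [1.960 × √(2 × 0.5 × 0.5) + 1.2816 × √(0.4 × 0.6 + 0.6 × 0.4)]² / 0.2² = (1.386 + 0.888)² / 0.04 = 129.3.

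So 130 per group, 260 in total, reproduces. Nothing below changes it.

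**2. Precision of the unadjusted difference.** With 40% attainment in both groups, SE = √(2 × 0.4 × 0.6 / 130) = 0.0608. The 95% half-width is 1.96 × 6.08 = 11.9 points.

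**3. Bias from residual imbalance.** The documents give no covariate effects, so these are assumptions: binary covariates with 50% prevalence, each shifting attainment by 15 to 20 points, and a 5-point difference in prevalence between groups, all in the same direction. Bias = number of covariates × imbalance × effect. Approximate size of the nominal 5% test = Φ(−1.96 + d) + Φ(−1.96 − d), with d = bias / 6.08.

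| Imbalanced covariates | Effect | Bias (points) | d | Size of unadjusted test |
|---|---|---|---|---|
| 1 | 15 | 0.05 × 15 = 0.75 | 0.12 | 5.2% |
| 1 | 20 | 0.05 × 20 = 1.0 | 0.16 | 5.3% |
| 3 | 15 | 3 × 0.75 = 2.25 | 0.37 | 6.6% |
| 3 | 20 | 3 × 1.0 = 3.0 | 0.49 | 7.8% |

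Simulation (130 per group, 20,000 runs per cell) agrees for three covariates: 6.4% and 7.6% unadjusted. The model with all three covariates fixed in advance gave 5.2% and 5.3%, and adjusted estimates were unbiased.

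**4. Cost of ignoring successful matching.** If all three covariates are matched exactly, the within-pair correlation is ρ = 3 × effect² × 0.25 / 0.24. The unpaired SE is too large by the factor 1/√(1 − ρ), and the true size is 2 × [1 − Φ(1.96 / √(1 − ρ))].

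| Effect | ρ | SE factor | True size |
|---|---|---|---|
| 15 points | 3 × 0.0225 × 0.25 / 0.24 = 0.070 | 1.037 | 4.2% |
| 20 points | 3 × 0.04 × 0.25 / 0.24 = 0.125 | 1.069 | 3.6% |

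So about 4%. Simulation under exact matching gave 4.0% for the unadjusted test and 4.9–5.1% for the adjusted one.

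**5. Power of the proposed analysis.** In 130 simulated pairs (6,000 runs), matched exactly on race and one disease flag and with one further covariate unmatched, a standardised risk difference with pair-clustered standard errors had power 90.6–93.8% at 40% vs 60%. Chi-square had 90.6–93.7%. Type I error was 4.7–5.7% and 3.8–5.1% respectively. Because the sizes differ, this shows no loss of power; it does not measure a gain.

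**The case against.** The strongest defence is that the plan already deals with confounding by design. Controls are chosen by an algorithm with balance checks, and of the person who runs it Section 8.4 says: "The statistician will have no knowledge of survival outcome, other outcome data, and genotype". The covariate sentence says an identified confounder will be entered, which is a one-way rule and not a search among models. It also follows a remark about ANOVA and does not name the primary endpoint.

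Much of this stands. A reader might infer that Section 8.3 permits choosing the most favourable model, and that type I error is therefore badly inflated. The documents do not support that. Taking the smallest p-value over every subset of three or four covariates gave 6.6–8.8% in simulation with no imbalance, and 7.7–11.3% with 5 points of imbalance in every covariate. Those runs leave out the matching and model a search that the text does not describe. With every covariate matched exactly, the smallest-p size was 4.9–5.5%. Neutral entry rules (imbalance at p < 0.10, or a change in the estimate of at least 1 point) stayed at 4.4–5.5%.

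Nor should much be read into analyst blinding. Section 9.5 says: "The interim analysis will be performed by an independent statistician who is blinded". Section 10.1 requires only that identifiers be removed from the analyst's data. The documents are silent on blinding of the final analyst; they do not say that this analyst sees outcomes before choosing covariates.

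Three things survive. Section 8.3 covers the primary endpoint, so its open adjustment clause is not confined to continuous outcomes. The matching variables are nowhere made part of the primary test. And unmatched prospective controls are a route to imbalance that the algorithm does not close.

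**Conclusion.** The point holds as a choice of the weaker analysis, with a modest effect. Under assumed covariate effects of 15 to 20 points and a 5-point residual imbalance, the unadjusted difference is biased by about 1 point (one covariate) to 3 points (three covariates in the same direction). That is 5% to 15% of the 20-point difference the study is sized to detect. Imbalances in opposite directions would partly cancel. Under exact matching the unadjusted test is slightly conservative, at about 4%. An analysis adjusted for the matching variables removes both effects.

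Two limits apply. Adjustment removes bias only for covariates on the list, so an important predictor left off it still matters. And how close the 8.4 matching will be is unknown, so the true effect may be smaller than these figures.

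The sample size of 260 is not undermined, and the documents do not show that the result will be selected.

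**What to change.** In Section 8.3, replace the sentence on confounders found during the analysis with one primary analysis of the primary proportion:
- a risk difference between groups, from a regression standardised over the study population;
- adjusted for age, race and the disease characteristics used by the 8.4 algorithm, each listed by name, with the list fixed before outcome data reach the analyst;
- with standard errors clustered on matched set, each unmatched prospective control counting as its own cluster.

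Label any covariate identified later as a sensitivity analysis. If Section 8.4 ends with more than one control per patient, the same specification can be used, but the power figures above cover 130 pairs only. How Day 3 and Day 7 combine into the primary proportion is a separate matter that this change does not settle.

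The cost is SAP wording and slightly more programming. No patients, visits or data are added, because the algorithm already needs these variables, and no power is lost. The team gives up post hoc choice of the primary model.

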8.4 Matching Strategy

As there are confounding variables, including age, race and disease state that may impact the results of the study, our study design incorporates an overall matching strategy, so that we can identify a well-matched control group. First, to control for differences in care over time, patients in the pharmacogenomic group will be matched to controls enrolled from 2010 to present. This time period was selected as there had been no major changes in standard of care or treatment regimen since 2010. After eligibility is met, control patients will be selected to match the pharmacogenomic group using a computerized matching algorithm that has been optimized to match baseline demographic and disease characteristics that have been identified a priori as likely to influence the treatment response to tacrolimus. To balance the trade-off between minimizing bias and maximizing matched sample size, a systematic approach will be conducted to identify the number of matched control patients for each patient in the pharmacogenomic group. This approach will include the following steps: 1) run the desired matching algorithm, starting with 1:1 (one control to one patient in the pharmacogenomic group) matching and iterating until the maximum desired number of potential controls per treated subject is reached; 2) for each iteration, test for covariate balance; and 3) generate numeric summaries and graphical plots of the balance statistics across all iterations in order to determine the optimal number (Linden and Samuels 2013).

The selection of patients for the control group using a matching algorithm will be conducted by an independent statistician in a blinded and unbiased manner. The statistician will have no knowledge of survival outcome, other outcome data, and genotype.

9 Safety and Adverse Events

Safety will be assessed throughout the study by evaluating physical exam, clinical chemistry, urinalysis, hematology, renal function, and incidence of adverse events (ie, graft rejection, graft loss, renal impairment, drug-related adverse events, tacrolimus toxicities, and death).

9.1 Definitions

Unanticipated Problems Involving Risk to Subjects or Others is defined as any incident, experience, or outcome that meets all of the following criteria:

- Unexpected in nature, severity, or frequency (ie, not described in study-related documents such as the IRB-approved protocol or consent form, the investigators brochure, etc.)
- Related or possibly related to participation in the research (ie, possibly related means there is a reasonable possibility that the incident experience, or outcome may have been caused by the procedures involved in the research,
- Serious (as defined below); “serious” is different than “severe” as reported in the NCI CTCAE criteria, which applies a grade to the AE.

Adverse Event

An AE is any symptom, sign, illness or experience that develops or worsens in severity during the course of the study. Intercurrent illnesses or injuries should be regarded as AEs. Abnormal results of diagnostic procedures are considered to be AEs if the abnormality:

- results in study withdrawal
- is associated with an SAE
- is associated with clinical signs or symptoms
- leads to additional treatment or to further diagnostic tests
- is considered by the investigator to be of clinical significance

Serious Adverse Event

All AEs are classified as serious or nonserious. A **serious AE** (SAE) is any AE that is:

- fatal
- life-threatening
- requires or prolongs hospital stay

- results in persistent or significant disability or incapacity
- a congenital anomaly or birth defect
- an important medical event

Important medical events are those that may not be immediately life threatening, but are clearly of major clinical significance. They may jeopardize the subject, and may require intervention to prevent one of the other serious outcomes noted above. For example, drug overdose or abuse, a seizure that did not result in in-patient hospitalization, or intensive treatment of bronchospasm in an emergency department would typically be considered serious.

All AEs that do not meet any of the criteria for serious are regarded as ***nonserious AEs***.

Preexisting Condition

A preexisting condition is one that is present at the start of the study. A preexisting condition should be recorded as an AE if the frequency, intensity, or the character of the condition worsens during the study period.

General Physical Examination Findings

At screening, any clinically significant abnormality should be recorded as a preexisting condition. At the end of the study, any new clinically significant findings/abnormalities that meet the definition of an AE must also be recorded and documented as an AE.

Abnormal Laboratory Values

A clinical laboratory abnormality should be documented as an AE if any one of the following conditions is met:

- The laboratory abnormality is not otherwise refuted by a repeat test to confirm the abnormality
- The abnormality suggests a disease and/or organ toxicity
- The abnormality is of a degree that requires active management; e.g. change of dose, discontinuation of the drug, more frequent follow-up assessments, further diagnostic investigation, etc.

Hospitalization, Prolonged Hospitalization or Surgery

Any AE that results in hospitalization or prolonged hospitalization should be documented and reported as an SAE unless specifically instructed otherwise in this protocol. Any condition responsible for surgery should be documented as an AE if the condition meets the criteria for an AE.

Neither the condition, hospitalization, prolonged hospitalization, nor surgery are reported as an AE in the following circumstances:

- Hospitalization or prolonged hospitalization for diagnostic or elective surgical procedures for a preexisting condition. Surgery should **not** be reported as an outcome of an AE if the purpose of the surgery was elective or diagnostic and the outcome was uneventful.
- Hospitalization or prolonged hospitalization required to allow efficacy measurement for the study.
- Hospitalization or prolonged hospitalization for therapy of the target disease of the study, unless it is a worsening or increase in frequency of hospital admissions as judged by the clinical investigator.

9.2 Recording of Adverse Events

AEs will be collected following kidney transplantation. AEs are recorded as part of routine standard of care for kidney transplant recipients.

At each contact with the subject, the investigator must seek information on AEs by specific questioning and, as appropriate, by examination. Information on all AEs should be recorded immediately in the source document. All clearly related signs, symptoms, and abnormal diagnostic procedures results should be recorded.

All AEs occurring during the study period must be recorded. The clinical course of each event should be followed until resolution, stabilization, or until it has been determined that the study treatment or participation is not the cause. SAEs that are still ongoing at the end of the study period must be followed up to determine

the final outcome. Any SAE that occurs after the study period and is considered to be possibly related to the study treatment or study participation should be recorded and reported immediately.

All AEs, both serious and nonserious, and deaths that occur during the patient's study participation will be recorded. All SAEs should be monitored until they are resolved or are clearly determined to be due to a patient's stable or chronic condition or intercurrent illness(es).

9.3 Reporting of Serious Adverse Events and Unanticipated Problems

Investigators must conform to the AE reporting timelines, formats, and requirements of the various entities to which they are responsible, but at a minimum those events that must be reported are those that are:

- related to study participation,
- unexpected, and
- serious or involve risks to subjects or others (see definitions, [Section 9.1](#)).

9.3.1 Investigator reporting

For reportable deaths, the initial submission to the IRB may be made by contacting the IRB Director or Associate Director. The AE/Unanticipated Problem Form is required as a follow up to the initial submission.

All AEs may be submitted on FDA Form 3500A or in a narrative format. If supplied as in a narrative format, the minimum information to be supplied is noted above at the beginning of [Section 9.3](#).

Any serious or unexpected event, which occurs to any patient in the course of their treatment on this study or within 30 days following cessation of treatment, must be reported immediately within 24 hours of the investigator learning of its occurrence. The immediate reports should be followed promptly by detailed, written reports. The Principal Investigator is responsible for reporting the SAEs to the FDA in accordance with 21 CFR 312.32 and 21 CFR 314.80. If required, an NCI Adverse Drug Reaction (ADR) form will be completed and copies sent to:

- Principal Investigator
- IRB
- UNC-CH Investigational Drug Service
- Protocol Office ADR file

For both serious and nonserious AEs, the investigator must determine both the intensity of the event and the relationship of the event to drug administration.

- Relationship to drug administration will be determined by the investigator responding yes or no to the question: Is there a reasonable possibility that the AE is associated with the drug?
- Intensity for each AE, including any lab abnormality, will be determined by using the NCI CTCAE, version 3.0, as a guideline, wherever possible.
(<http://ctep.cancer.gov/forms/CTCAEv3.pdf>)

